### 6.3 Management of Clinical Events

#### 6.3.1 Management of Hyperglycemia

Guidance for TAK-228 dose management in the event of hyperglycemia is provided in the table below.

Table 5: Management of Hyperglycemia

Grade	Description	Treatment	TAK-228 Dose Modification
1	Fasting blood sugar > ULN–160 mg/dL	Continue close monitoring of blood sugars. Consider initiation of oral hypoglycemic agent and/or insulin if not well controlled on oral agent.	None.
2	Fasting blood sugar > 160–250 mg/dL	Initiate oral hypoglycemic agent and/or insulin if not well controlled on oral agent.	None.
≥3	Fasting blood sugar > 250 mg/dL	Initiate oral hypoglycemic agent and/or insulin.	Hold drugs until ≤ Grade 2. Resume TAK-228 based on timing of recovery: ≤ 1 week: resume at same dose and schedule; >1 but ≤2 weeks: reduce TAK-228 by 1 dose level >2 weeks: discontinue subject from study

#### Prevention/Prophylaxis

- Follow fasting serum glucose levels during clinic visits.
- Monitor home glucometer test results.
- Check HbA1c levels every 3 months during therapy.

- 
- Life-style modifications, as appropriate (balanced diet, limit alcohol consumption, increase physical activity).
  - Most episodes of Grade 1 and 2 hyperglycemia respond quickly to oral metformin.
  - Early initiation of therapy is recommended to prevent higher grade hyperglycemia.
  - Fasting blood glucose levels  $\geq 150$  mg/dL by glucometer should be followed by closer monitoring of serum glucose and possible intervention.
- 

Abbreviations: dL = deciliters; mg = milligrams; ULN = upper limit of normal.

On the basis of the clinical experience in TAK-228 trials, most episodes of hyperglycemia observed occurred within the first 60 days after initiation of treatment with TAK-228 and have been either Grade 1 or Grade 2, and have responded quickly to oral metformin. Hyperglycemia has not been dose-limiting since the institution of a standard regimen for early treatment of hyperglycemia.

All subjects developing hyperglycemia during the study should have their glucose closely monitored by study staff. The site investigator may choose to continue close monitoring of subjects who develop Grade 1 hyperglycemia (fasting glucose  $>ULN \leq 160$  mg/dL) or, alternatively, consider initiating treatment with an oral hypoglycemic agent, such as metformin. All subjects with  $\geq$ Grade 2 hyperglycemia (fasting glucose  $>160$  mg/dL) must be treated aggressively with oral hypoglycemic agents and/or insulin as clinically indicated. The site investigator should consult an endocrinologist, if needed, to aid in optimizing the subject's hyperglycemia treatment plan.

It is recommended that subjects be initially treated with a fast acting insulin sensitizer such as metformin at 500 mg orally QD, and titrate up to a maximum of 1000 mg orally BID as needed. Concurrent addition to metformin of DPP-4 inhibitors (eg, sitagliptin or vildagliptin) and/or insulin should also be considered. Oral sulfonylureas (eg, glipizide or glyburide) should be used with caution, due to the higher risk of inducing hypoglycemia in subjects. The dose of oral hypoglycemic agents should be adjusted in subjects with renal insufficiency. In addition, subjects should be encouraged to follow a low carbohydrate diet once hyperglycemia is first observed. If any fasting serum glucose reading performed at the site indicates hyperglycemia ( $>ULN$  or  $\geq 110$  mg/dL), the study staff should first confirm that the subject was fasting at the time of blood specimen collection (ie, nothing by mouth for at least 8 hours before collection).

### **In-Home Daily Fasting Glucose Monitoring**

In addition to obtaining fasting glucose levels at the clinic visits as outlined in the Schedule of Events, all subjects receiving TAK-228 will be given a glucometer to monitor their daily FBG levels at home. The level should be collected daily, predose on dosing days, and at approximately the same time each day.

Prior to initiating treatment, the subject will be provided an in-home glucometer. Subjects will be trained on proper use of the glucometer and instructed to collect a daily FBG level every morning (predose on dosing days), starting on Cycle 1 Day 2. Subjects will be instructed to bring the glucometer with them to each study visit so that the data collected can be reviewed and recorded in the source documents. Site investigators will be responsible for reviewing the home glucose monitoring logs for hyperglycemia.

The subject will be instructed to contact the site immediately if the value is abnormal (ie,  $\geq 150$  mg/dL) for further instructions on the management of their hyperglycemia. Hyperglycemia observed during home glucose monitoring should be confirmed in the clinic. If no irregularities in the fasting blood glucose level are observed during a minimum of 2 consecutive months, then the frequency of in-home fasting blood glucose testing can be reduced to a minimum frequency of once weekly, depending on the site investigator’s judgment and approval. Subjects will continue to notify the site investigator of fasting blood glucose levels that exceed 150 mg/dL and, if blood glucose levels are not well controlled, or if the subject requires either oral hypoglycemic agents or insulin to control blood glucose levels, then the frequency of in-home testing of FBG levels will be reinstated to daily.

### 6.3.2 Management of Noninfectious Pneumonitis

Guidance for TAK-228 dose management in the event of noninfectious pneumonitis is shown in the table below.

Table 6: Management of Non-infectious Pneumonitis

Grade	Description	Treatment	TAK-228 Dose Modification
1	Asymptomatic: Radiographic findings only	Rule out infection and closely monitor.	None.
2	Symptomatic: Not interfering with ADLs	Rule out infection and consider treatment with corticosteroids until symptoms improve to $\leq$ Grade 1.	Interrupt TAK-228 treatment: When symptoms $\leq$ Grade 1, re-initiate TAK-228 treatment at a dose reduction Discontinue TAK-228 treatment if failure to recover within 4 weeks.
3	Symptomatic: Interfering with ADLs; Requires administration of O 2	Rule out infection and consider treatment with corticosteroids until symptoms improve to $\leq$ Grade 1.	Interrupt TAK-228 treatment until symptoms resolve to $\leq$ Grade 1. Consider re-initiating TAK-228 treatment at a dose reduction If toxicity recurs at Grade 3, discontinue TAK-228 treatment.
4	Life-threatening: Ventilatory support indicated	Rule out infection and consider treatment with corticosteroids.	Discontinue TAK-228 treatment.

Abbreviations: ADL = activities of daily living; O2 = oxygen gas.

### 6.3.3 Management of Hyperlipidemia

Guidance for TAK-228 dose management in the event of hyperlipidemia is shown in the table below.

Table 7: Management of Hyperlipidemia

Grade	Description	Treatment	TAK-228 Dose Modification
1	Cholesterol: > ULN - 300 mg/dL Triglycerides: > 150 - 300 mg/dL	None.	None.
2	Cholesterol: > 300 – 400 mg/dL Triglycerides: > 300 - 500 mg/dL	Treat hyperlipidemia according to standard guidelines. Triglycerides $\geq$ 500 mg/dl should be treated urgently due to risk of pancreatitis.	Maintain dose if tolerable.  If toxicity becomes intolerable, interrupt TAK-228 dosing until recovery to $\leq$ Grade 1. Reinitiate at same dose.
3	Cholesterol: > 400 - 500 mg/dL Triglycerides: > 500 - 1000 mg/dL	Same as for Grade 2.	Hold dose until recovery to $\leq$ Grade 1, then restart at a dose reduction
4	Cholesterol: > 500 mg/dL Triglycerides: > 1000 mg/dL	Same as for Grade 2.	Same as for Grade 3.

**Prevention/Prophylaxis**

- Life-style modifications, as appropriate (balanced diet, limit consumption of alcoholic beverages, increase physical activity).

Abbreviations: dL = deciliters; mg = milligrams; ULN = upper limit of normal.

**6.3.4 Management of Oral Mucositis**

Guidance for TAK-228 dose management in the event of oral mucositis is provided in the table below.

Table 8: Management of Oral Mucositis

Grade	Description	Treatment	TAK-228 Dose Modification
1	Asymptomatic or mild symptoms	Non-alcoholic mouth wash or 0.9% salt water rinse; Consider topical corticosteroids at earliest signs of mucositis.	None.
2	Moderate pain, not interfering with oral intake  Modified diet indicated	Topical analgesic mouth treatments; Topical corticosteroids; Initiate antiviral or antifungal therapy, if indicated.	Maintain dose if tolerable.  If toxicity becomes intolerable, interrupt TAK-228 dosing until recovery to $\leq$ Grade 1. Reinitiate at same dose.
3	Severe pain, interfering with oral intake	Same as for Grade 2; Consider intra-lesional corticosteroids.	Hold dose until recovery to $\leq$ Grade 1, then restart at a dose reduction

---

4	Life-threatening consequences	Same as for Grade 2. Consider intra-lesional corticosteroids.	Discontinue treatment.
---	-------------------------------	------------------------------------------------------------------	------------------------

---

**Prevention/Prophylaxis**

- Consider initiation of a non- alcoholic mouth wash or 0.9% salt water rinses 4-6 times daily with start of therapy before signs of mucositis develop.
  - Avoid using agents containing hydrogen peroxide, iodine, and thyme derivatives in management of stomatitis as they may worsen mouth ulcers.
-

### 6.3.5 Management of Rash

Guidance for TAK-228 dose adjustment for the event of rash is provided in the table below

Table 9: Management of Rash

Grade	Description	Treatment	TAK-228 Dose Modification
≤ 2	Macules/papules covering ≤ 30% body surface area with or without symptoms	Consider treatment with topical steroid cream/ointment and/or oral anti-histamines or antibiotics.	None.
≥ 3	Macules/papules covering > 30% body surface area with or without symptoms	Consider treatment with topical steroid cream/ointment, oral antihistamines, oral antibiotics, and/or pulsed steroids.	Hold until ≤ Grade 2; Resume TAK-228 based on timing of recovery and severity of symptoms: ≤ 3 weeks: reduce dose by 1 dose level; > 3 weeks and severely symptomatic: stop TAK-228 and discontinue subject from the study.

Subjects who develop Grade 4 rash should permanently discontinue study treatment, unless they derive clinical benefit as determined by the site investigator, in which case they may be retreated at a reduced dose level after recover to ≤ Grade 1 severity. Grade 4 rash is defined as rash acneiform and/or papulopustular with papules and/or pustules covering any % body surface area, which may or may not be associated with symptoms of pruritus or tenderness, AND are associated with extensive superinfection requiring with intravenous (IV) antibiotics indicated; life threatening consequences (NCI CTCAE Version 4.03, effective date 14 June 2010).

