### 6.1 TAK-228 Dose Modifications

TAK-228 administration should be withheld for treatment-related adverse events that are Grade 3 or higher, despite supportive treatment per standard clinical practice. If the event resolves to Grade 1 or Grade 2 for hyperglycemia or rash or to baseline values within 2 weeks of interrupting treatment, then the subject may resume study treatment at a dose reduced by 1 level (see Table below). If study drug administration is delayed for more than 4 weeks (28 consecutive days) due to non-resolving study drug-related grade 3 toxicity despite supportive treatment per standard clinical practice, or more than 3 dose reductions of study drug are required in a subject, then study drug treatment should be stopped, the subject discontinued from the study, and the EOT visit completed within 30 days ( $\pm 7$ ) after the last dose of study drug.

If study drug administration is delayed for more than 6 weeks (42 consecutive days) due to non-treatment related adverse events, then study drug treatment should be discontinued, and EOT visit completed within 30 days ( $\pm 7$  days) after the last dose of study drug

If study drug is delayed for either less than 4 weeks (28 consecutive days) due to non-resolving study drug-related grade 3 toxicity or less than 6 weeks (42 consecutive days) due to non-treatment related adverse events, subjects should skip the dosing cycles missed and when if treatment is resume, this should be at the next scheduled dosing cycle.

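### Grade 4 rash: the ≥ 3 row of Table 9 and Section 6.1 allow a reduced-dose restart at Grade 2, the paragraph under Table 9 does not, and nothing links the three passages

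*Combined protocol and SAP*

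**What the plan says.** Three passages bear on Grade 4 rash.

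- **Section 6.3.5, Table 9, row labelled ≥ 3.** The row describes "Macules/papules covering > 30% body surface area with or without symptoms". Its instruction is "Hold until ≤ Grade 2; Resume TAK-228 based on timing of recovery and severity of symptoms". Recovery within 3 weeks leads to a restart one dose level lower. The only stopping branch is "> 3 weeks and severely symptomatic: stop TAK-228 and discontinue subject from the study".
- **Section 6.3.5, paragraph under Table 9.** "Subjects who develop Grade 4 rash should permanently discontinue study treatment, unless they derive clinical benefit as determined by the site investigator". Where benefit is found, retreatment is possible at a lower dose, but only once the rash has come down to Grade 1 or below. The paragraph defines Grade 4 as "rash acneiform and/or papulopustular with papules and/or pustules covering any % body surface area", together with extensive superinfection for which intravenous antibiotics are indicated, and life-threatening consequences.
- **Section 6.1, general rule.** "TAK-228 administration should be withheld for treatment-related adverse events that are Grade 3 or higher". The restart condition begins "If the event resolves to Grade 1 or Grade 2 for hyperglycemia or rash". If it is met within 2 weeks of interruption, the subject may resume one level lower.

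The row and Section 6.1 contain no Grade 4 exception for rash and no pointer to the paragraph. The paragraph does not say that it overrides either of them.

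**The concern.** Both the label ≥ 3 and the phrase Grade 3 or higher include Grade 4. Read literally, the row and Section 6.1 therefore allow a restart that the adjacent paragraph rules out, either altogether (no clinical benefit) or until a lower grade is reached (with benefit).

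The documents themselves define this event by life-threatening consequences. A site that works from the table or from Section 6.1 alone could give TAK-228 again, at a reduced dose, to a subject whom the paragraph says to stop. Sites could also handle the same event differently, and reasons for discontinuation would then be recorded inconsistently. A secondary link is that Section 12.2.1 closes the window for objective response at progression or at cessation of trial therapy, whichever is first, so the date of stopping has some bearing on the primary endpoint.

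**Working it through.** There is no figure to reproduce. The check is a comparison of texts.

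| | Table 9, row ≥ 3 | Section 6.1 | Paragraph under Table 9 |
|---|---|---|---|
| Covers Grade 4 by wording? | Yes, by label | Yes | Yes, by name |
| Event described | Macules/papules, > 30% body surface | Any treatment-related event | Acneiform/papulopustular, any % body surface, superinfection |
| Default | Hold, then resume | Withhold, then may resume | Permanent discontinuation |
| Recovery grade for restart | ≤ 2 | 1 or 2 | ≤ 1 |
| Time limit for restart | ≤ 3 weeks | Within 2 weeks | None stated |
| Clinical benefit needed? | No | No | Yes |
| Dose on restart | One level lower | One level lower | Reduced level |

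Applying the three passages to cases:

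1. **Grade 4, Grade 2 reached in 10 days, no clinical benefit determined.** Ten days is inside both windows (14 and 21 days). The row resumes one level lower, Section 6.1 permits the same, and the paragraph stops treatment permanently. The default actions conflict.
2. **Same course, benefit determined.** The row and Section 6.1 allow restart at Grade 2. The paragraph waits for Grade 1. All give a reduced dose, so the difference is one grade of recovery.
3. **Grade 4, Grade 1 reached in 10 days, benefit determined.** All three allow a reduced-dose restart. There is no conflict.

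**Label against description.** The row's label takes in Grade 4, but its description does not match the paragraph's Grade 4 event. The lesion type differs, the paragraph sets no minimum area, and the row's treatment column lists oral but not intravenous antibiotics. The overlap therefore comes mainly from the label.

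**How other tables handle Grade 4.** Tables 6, 8 and 14 give it its own row. Table 13 keeps a combined ≥ 3 row but puts the Grade 4 exception inside the same cell. Table 9 does neither.

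**Two further mismatches for rash, also present at Grade 3.**

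- *Recovery to Grade 2 after 2 but within 3 weeks.* The row resumes one level lower. The resume sentence in Section 6.1 no longer applies.
- *Recovery after more than 3 weeks, not severely symptomatic.* Neither branch of the row applies. Section 6.1 stops treatment only after a delay of more than 4 weeks for non-resolving drug-related Grade 3 toxicity. For shorter delays it says at which point in the schedule dosing restarts if it does, but not whether it should.

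**The case against.** The strongest answer is that the paragraph is a specific exception to a general row. It sits directly under the table, in the same section, and names and defines Grade 4. Table 13 pairs a ≥ 3 rule with a Grade 4 exception in nearly the same words, and there the two plainly coexist. The row's description is not the Grade 4 event either. Section 6.1 is general guidance that permits resumption and does not require it, and Section 5.5 lets treatment end for unacceptable adverse events. Combined ≥ 3 rows are common in this protocol (Tables 5, 10, 12 and 13), so the format is not in itself a fault.

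Most of this stands, and the exception is the natural reading. It does not remove the point. Nothing in the row or in Section 6.1 tells the reader that an exception exists, and Section 6.1 is in a different place. The Table 13 parallel shows how the exception could have been placed inside the cell; in Table 9 it was left outside.

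A reader might infer three stronger things that the documents do not support:

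- *That Grade 4 rash has two opposite rules throughout.* The defaults are opposite only where the site investigator finds no clinical benefit. With benefit, the passages differ in recovery grade alone.
- *That a subject faces full re-exposure or none.* Every restart route for this event is at a reduced dose.
- *That the primary endpoint is materially affected.* The link through cessation of therapy exists, but the documents give no basis for estimating its effect.

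The missing instruction after 3 weeks is also partly bounded by the 4-week limit in Section 6.1, although that limit is worded for Grade 3.

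**Conclusion.** The point holds as an internal inconsistency in scope and recovery grade. By their wording, the ≥ 3 row of Table 9 and Section 6.1 cover Grade 4 rash and allow a reduced-dose restart at Grade 2. The paragraph under Table 9 sets permanent discontinuation as the default and asks for Grade 1 or below, plus clinical benefit, before any retreatment.

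Its size is one grade in the recovery threshold, and a different default action when benefit is not determined. The number of patients is likely small, but the documents give no rate of Grade 4 rash from which to derive it. The conclusion assumes that the rash is treatment-related, so that Section 6.1 applies, and that some site staff will follow the row label or Section 6.1 as written without carrying over the paragraph. It takes no view on which clinical rule is correct.

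Because the event is defined as life-threatening and the correction is easy, the passages should be reconciled even though the intended meaning can probably be guessed.

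**What to change.** Reconcile the three passages so that the scope of the Table 9 row, the Grade 4 paragraph and the rash wording in Section 6.1 agree on the default action and the recovery grade for Grade 4. The form can be light: for example, limit the row to Grade 3, or add a Grade 4 cross-reference in both the row and Section 6.1. Make the row's description consistent with whatever grades it is meant to cover.

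In the same edit:

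- reconcile the rash resume windows (within 2 weeks in Section 6.1, 3 weeks or less in Table 9);
- give an instruction for recovery after more than 3 weeks without severe symptoms.

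The clinical team decides which rule stands in each case.

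The cost is a few lines of text. There is no change to data collection, sample size or analysis. It can travel with the next amendment, which participating institutions must in any case take through their own IRBs, with 90 days from receipt under Appendix E.

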#### Prevention/Prophylaxis:

Rash should be managed aggressively. The site investigator should consider consulting a dermatologist or other specialist, if needed. A skin biopsy at the site of rash should be considered as soon as possible after the initial episode.

### 6.3.6 Management of Nausea and/or Vomiting

Guidance for TAK-228 dose adjustment for the event of nausea and/or vomiting is provided in the table below.

Table 10: Management of Nausea and/or Vomiting

Grade	Description	Treatment	TAK-228 Dose Modification
≤ 2	Loss of appetite with or without decreased oral intake; 1-5 episodes of vomiting within 24 hours	Maximize anti-emetic therapy; Consider IV fluid hydration.	None.
≥ 3	Inadequate oral intake; ≥ 6 episodes of vomiting within 24 hours	Maximize anti-emetic therapy; Initiate tube feeding, IVF, or TPN.	If experienced for ≤72 hours, hold TAK-228 until ≤ Grade 1, then resume TAK-228 without dose modification. If experienced for >72 hours despite optimal therapy, hold TAK-228 until ≤ Grade 1, then resume treatment with the dose of TAK-228 reduced by 1 level.

#### Prevention/Prophylaxis

Prophylactic use of anti-emetic, anti-nausea, and anti-diarrheal medications are encouraged and may be used before each dose of TAK-228 as needed throughout the study.

Abbreviations: IV = intravenous; IVF = intravenous fluids; TPN = total parenteral nutrition

### 6.3.7 Management of Cardiac Events

#### 6.3.7.1 Management of Cardiac Instability

For subjects showing signs of cardiac instability after TAK-228 dosing, additional monitoring onsite before clinic discharge should be considered.

#### 6.3.7.2 Management of Left Ventricular Dysfunction

Guidance for TAK-228 dose adjustment for the event of left ventricular dysfunction is provided in the table below.

Table 11: Management of Left Ventricular Dysfunction

Grade	Description	TAK-228 Dose Modification
1	Asymptomatic decline in LVEF > 15% from baseline values OR; LVEF > 10%-15% from baseline values and is below institution's LLN	No change; continue TAK-228 at same dose and schedule.
≥ 2	Symptomatic cardiac dysfunction/congestive heart failure	Discontinue treatment.

Abbreviations: LLN = lower limit of normal; LVEF = left ventricular ejection fraction.

### 6.3.7.3 Management of QTc Prolongation

Guidance for TAK-228 dose adjustment for the event of QTcF prolongation is provided in the table below.

Table 12: Management of QTc Prolongation

Grade	Description	Treatment	TAK-228 Dose Modification
2	480 ms < QTcF < 501 ms	Evaluate for other possible causes (eg, electrolyte disturbance, concomitant medication, etc.)	None; continue TAK-228 at the same dose and schedule.
≥ 3	QTcF ≥ 501 ms	Evaluate for other possible causes (eg, electrolyte disturbance, concomitant medication) a ; Consider a formal consult by a cardiologist; Notify the study doctor; Additional ECGs may be performed at intervals that the treating physician deems clinically appropriate until repeated QTc measurements fall or are below the threshold interval that triggered the repeat measurement.	TAK-228 should be interrupted.  Subjects who experience persistent symptomatic Grade 3 or Grade 4 QTc prolongation without another cause should permanently discontinue study treatment.

Abbreviations: ECG = electrocardiogram; IV = intravenous; ms = milliseconds; QTc = QT interval corrected for heart rate

a A list of medications known to prolong QTc can be found at [www.torsades.org](http://www.torsades.org) and [www.QTdrugs.org](http://www.QTdrugs.org).

